## 4.3 Study Objectives

## 4.3.1 Main Objectives:

The main objectives of this study are:

- (i) To assess the diagnostic accuracy of three commercially-available rapid tests for Candida infection (beta-D-glucan and two PCR-based tests) in the UK critical care setting.
- (ii) To develop a test-based protocol that could be used to guide antifungal drug prescribing in this setting.

### 4.3.2 Secondary Objectives:

The secondary objectives of this study are:

- (i) To model the clinical effectiveness of implementing the resultant protocol in UK ICUs as a tool for more appropriately targeting antifungal therapy.
- (ii) To estimate the proportion of patients currently receiving empirical antifungal therapy in UK ICUs for whom treatment is not clearly indicated.
- (iii) To develop a test-based protocol using the index tests (alone or in combination), as a strategy for early cessation of empirical antifungal treatment, with assessment of its expected cost-effectiveness modelled on test accuracy, disease prevalence and clinical/economic outcomes in this patient group.
- (iv) To assess patient and physician risk preferences, for using the tests to discontinue presumptive antifungal therapy.
- (v) To use these data, along with value of information analysis, to estimate the potential utility of, and propose the design for, a future randomised trial.

Doc No: TM09-LB01 Protocol Version 8.0 Final\_27.05.2021 Page 15 of

#### 5. OUTCOME MEASURES

## **5.1 Primary Outcome Measure**

The primary outcome measure is negative predictive value for each index test. Other diagnostic test accuracy measures will also be reported to support this (comprising sensitivity, specificity, positive predictive value and positive/negative likelihood ratios). The analysis for this primary outcome will be based on an international consensus reference standard for proven invasive fungal disease, applied for Candida infection.

## 5.2 Secondary Outcome Measures

Secondary outcome measures of the study are based on:

- (i) Measures of diagnostic test accuracy, for each test alone and in combination, based on an international consensus reference standard for proven invasive fungal disease, applied for Candida infection. These will comprise sensitivity, specificity, positive/negative predictive values and positive/negative likelihood ratios.
- (ii) Measures of diagnostic test accuracy, for each test alone and in combination, based on an international consensus reference standard for proven and probable invasive fungal disease, applied for Candida infection.
- (iii) Estimated proportion of patients receiving systemic antifungal therapy in this cohort for whom treatment is unnecessary, derived from the reference standards used. Estimated number of days' avoidable antifungal treatment if negative index test results were used to stop treatment.
- (iv) Development of a test-based protocol using the index tests (alone or in combination), as a strategy for early cessation of empirical antifungal treatment. Assessment of its expected cost-effectiveness modelled on test accuracy, disease prevalence and clinical/economic outcomes in this patient group.
- (v) Risk preferences of clinicians and patients supporting an evaluation of barriers to test adoption.

Doc No: TM09-LB01 Protocol Version 8.0 Final\_27.05.2021 Page 16 of

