## PROTOCOL AUTHORISATION

Protocol Title	Antifungal stewardship opportunities with rapid tests for fungal infection in critically ill patients.
Protocol Acronym (if applicable)	A-Stop
Protocol Number	B17/23
Protocol Version Number/Date	v8.0_27/05/2021
Protocol Amendments	v1-v2 key changes 9.2.1 Blood sampleincreased from approximately 12mL to approximately 14mL in adult participants. v2-v3 key changes 8.0 Informed consent -removal of reference to Scottish sites/processes 9.1 Schedule of assessments -timing of standard care blood culture changed to within 24 hours of starting antifungal treatment -additional risk factors added for assessment of probable Candida infection 14.9 Patient confidentiality -an exception to unique trial identifier pseudonymisation is noted as NICTU determining participant mortality via the participant's GP v3-v4 key changes Inclusion criterion changed- Prescribed systemic antifungal therapy, for suspected or confirmed Candida infection, during the preceding 24 hours. Exclusion criterion added- Treatment with antifungal therapy for superficial Candida infection (e.g. thrush) 7.1 - Confirmation of eligibility by a person suitably qualified by education, training or experience. 9.2.1 - Blood sampling: For children, the preferred research sample volume is 4mL, however, this may be either increased or decreased as deemed appropriate by the clinical team up to a maximum of 14mL 9.2.1- Blood sampling: research blood should be obtained as soon as possible within 24 hours of the standard care blood culture. v4-v5 key changes Exclusion criterion removed- Treatment with antifungal therapy for superficial Candida infection (e.g. thrush) 9.1 Glucocorticosteroid treatment paediatric prednisolone equivalent dose added  v6 withdrawn  v5 - v7 key changes 1_Study Summary: Exclusion criteria: added Proven or suspected active infection with COVID-19 Target Sample Size: reduced to 1250

Doc No: TM09-LB01 Protocol Version 8.0 Final\_27.05.2021 Page 2 of 42

Study Duration: extended to 63 months

Co-investigators:

[name] replaced by [name] as Co-investigator.

Trial Statistician: replaced as [name].

6 Study design

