#### 7.1.1 Inclusion criteria:

- 1. Adults and children >4 weeks old.
- 2. Admitted to a UK ICU (level 2 or 3).
- 3. Prescribed systemic antifungal therapy, for suspected or confirmed Candida infection, during the preceding 24 hours.

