#### 7.1.2 Exclusion criteria:

- 1. More than 24 hours systemic antifungal therapy in the preceding 7-days.
- 2. Treatment with antifungal therapy for proven or suspected mould infection (e.g. aspergillosis).
- 3. Neutropenia (absolute neutrophil count <0.5x10^9/L) during preceding 28 days.
- 4. Acute leukaemia or within 12 months of bone-marrow transplantation.
- 5. Hospitalised prisoners.
- 6. Previously enrolled in this study.
- 7. Proven or suspected active infection with COVID- 19.

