#### **Baseline**

- · Age and gender
- Inclusion and exclusion criteria.
- Hospital admission date and location of patient prior to admission
- ICU admission date and main diagnosis
- Date research blood sample obtained for index tests and reference standard test
- Candida colonisation status at non-sterile anatomic sites, as determined by local laboratory testing in the course of normal clinical care
- Drug, dose and start date of systemic antifungal therapy
- Indication for starting antifungal therapy (e.g. for suspected or proven Candida infection)
- Patient characteristics triggering suspicion of Candida infection (e.g. fever, leucocytosis, increasing inotrope requirement, new or worsening organ failure, signs of intra-abdominal sepsis, failure to demonstrate improvement with broad-spectrum antibacterial treatment)
- Severity of illness indicators: APACHE II on admission to ICU (ICNARC case mix programme number) and SOFA score (adults) & PELOD-2 score (children- when available) on the day of recruitment.

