#### Assessed by site staff:

- Outcome of reference standard for proven fungal disease, as applied to Candida infection (based on data collected/laboratory results from day of enrolment). This will comprise:
  - Blood culture, yielding Candida species, drawn within 24 hours of starting antifungal treatment; AND/OR
  - Culture showing Candida species in specimen obtained by a sterile procedure from a normally sterile site (excluding urine). This includes a drain placed within 24 hours before sampling.

A blood culture will be drawn from each participant within 24 hours of starting antifungal treatment, usually in the course of standard clinical care, in accordance with usual practice for patients started on antifungal treatment. Specimens from

Doc No: TM09-LB01 Protocol Version 8.0 Final\_27.05.2021 Page 23 of

other normally sterile sites will be obtained as considered appropriate by the attending physician in the course of normal clinical care.

- Outcome of any blood cultures yielding Candida species taken +/-7 days from obtaining the research blood sample.
- Host factors and clinical findings pertinent to classification using a recently constructed consensus definition for probable Candida infection. Data collection for this classification will comprise:

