#### **HOST FACTORS:**

- Glucocorticosteroid treatment (prednisolone equivalent of ≥ 20 mg/day or >1mg/kg prednisolone for children under 20kg)
- Treatment with other systemic immunosuppressant drugs
- History of diabetes
- Major surgery during current ICU episode
- Renal replacement therapy
- Neutrophil abnormality (e.g. inherited neutrophil deficiency)
- Impaired gut wall integrity (Recent abdominal surgery, biliary tree abnormality, recurrent intestinal perforations, ascites, mucositis, severe pancreatitis, parenteral nutrition)
- Impaired cutaneous barriers to bloodstream infection (Presence of central vascular access device, hemodialysis)
- Colonization with Candida species in  $\geq$  2 sites (Respiratory tract secretions, stool/rectal swab, skin, wound sites, urine and drains that have been in place for ≥24 hours)
- Solid organ transplant

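### Systemic treatment for superficial or urinary Candida is eligible, yet outcome (iii) can count it as unnecessary by standards that assess only invasive disease

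*Protocol*

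**What the plan says.** **Who enters.** Inclusion criterion 3 (Protocol 7.1.1) reads: "Prescribed systemic antifungal therapy, for suspected or confirmed Candida infection, during the preceding 24 hours". It is not limited to invasive disease. Of the seven exclusions in 7.1.2, the only one that turns on what the antifungal was given for concerns mould infection. The amendment log is history only, but it agrees with the current list: "Exclusion criterion removed- Treatment with antifungal therapy for superficial Candida infection (e.g. thrush".

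**How disease is classified.** Sections 5.1 and 5.2 describe both reference standards as standards for invasive fungal disease. Under section 9.1 the proven standard needs a blood culture yielding Candida, or a culture from a "specimen obtained by a sterile procedure from a normally sterile site (excluding urine"), so a urine culture cannot make a case proven. For the probable standard, section 9.1 collects host factors, clinical findings and mannan/anti-mannan results. Urine enters there only as one of several colonisation sites: "Respiratory tract secretions, stool/rectal swab, skin, wound sites, urine and drains that have been in place for" at least 24 hours.

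**What counts as unnecessary.** Outcome (iii) in section 5.2 estimates the proportion of treated patients "for whom treatment is unnecessary, derived from the reference standards used". Section 11.4.1 takes the same proportion into the effectiveness model, as a range over the two standards. Avoidable days follow from a negative index test, with no condition on indication.

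**How the models use it.** In section 11.4.1, benefit is unnecessary treatment avoided and disadvantage is necessary treatment stopped. Section 11.4.2 describes true negatives as patients without, and not at risk of, fungal infection.

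**What is recorded.** The baseline list in section 9.1 includes "Indication for starting antifungal therapy (e.g. for suspected or proven Candida infection"). Nothing in outcome (iii), 11.4.1 or 11.4.2 uses this item, and it is not a listed subgroup in 11.5.2.

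**The concern.** Eligibility and the yardstick for necessity cover different conditions. Eligibility covers Candida infection of any kind that is treated systemically. The yardstick asks only whether invasive disease was present. For a patient treated for a confirmed urinary or superficial infection, a negative result on that yardstick says nothing about the condition treated, yet outcome (iii) reads it as evidence that treatment was unnecessary.

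The label carries forward. If such a patient is index-negative, the remaining treatment days count as avoidable. The effectiveness model scores stopping as benefit with no offsetting disadvantage. The economic model places the patient among those with no fungal infection, which is not true of someone with a confirmed non-invasive one. At stake are a named secondary outcome and the benefit side of both models.

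**Working it through.** **Inputs from Protocol 11.1:** N = 1250, 5% dropout, 4% prevalence, sensitivity 95%, specificity 92%.

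**The plan's own counts.** 1250 × 0.95 = 1187.5, stated as 1188. 1187.5 × 0.04 = 47.5, stated as 48. Both reproduce, and the stated values are used below.

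**Proportion unnecessary as written, proven standard.** (1188 − 48)/1188 = 1140/1188 = 96.0%. This does not depend on why anyone was treated.

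**Assumptions.** The protocol does not give the share *f* of the cohort treated for a non-invasive Candida indication, so 2%, 5% and 10% are shown. It is assumed that none of the group meets the invasive standard, that specificity in the group is the planned 92%, and that treatment length equals that of other non-infected patients.

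| Quantity | Formula | f = 2% | f = 5% | f = 10% |
|---|---|---|---|---|
| Patients in group, g | 1188 × f | 24 | 59 | 119 |
| Index-negative in group | 0.92 × 1188 × f | 22 | 55 | 109 |
| Share of non-infected patients' avoidable days | (0.92 × 1188 × f)/(0.92 × 1140) | 2.1% | 5.2% | 10.4% |
| Unnecessary, group out of numerator only | (1140 − g)/1188 | 94% | 91% | 86% |
| Unnecessary, group out of both | (1140 − g)/(1188 − g) | 95.9% | 95.7% | 95.5% |

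The last two rows answer different questions. The numerator-only row treats every member of the group as not unnecessarily treated, so it is a lower bound. The other row gives the proportion among patients whom the standards can assess.

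**Primary NPV.**
- As planned: (0.96 × 0.92)/(0.96 × 0.92 + 0.04 × 0.05) = 0.8832/0.8852 = 99.77%.
- Without a 10% group: prevalence is 48/(1188 − 119) = 48/1069 = 4.49%, and NPV = (0.9551 × 0.92)/(0.9551 × 0.92 + 0.0449 × 0.05) = 99.75%.

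**The case against.** Five points can be made in the protocol's defence.

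1. *Some of these patients can be classed as probable.* Colonisation at two or more sites, which may include urine, skin and wounds, is a host factor. So are central vascular access, renal replacement therapy and parenteral nutrition, and mannan results also contribute. This stands. A reader might infer that the whole group is negative on both standards, so that the planned range cannot help. The documents do not support that. The problem is clearest under the proven standard and applies under proven plus probable only to those who do not meet the probable criteria.

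2. *The headline proportion need not move much.* This stands. A reader might infer an upward bias of up to ten points from the 86%, but that figure depends on keeping the full denominator. With the group out of both, the change at a 10% share is about half a point.

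3. *The group may be very small.* Section 7.3 speaks of treatment started presumptively, and section 4.3.2 of empirical therapy. Neither wording says invasive, and criterion 3 also admits confirmed infection, so the group is not excluded. Its size remains unknown.

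4. *The primary outcome is safe.* This stands. A reader might infer that NPV is materially inflated, or that these patients are near-certain true negatives. The NPV shift is 0.02 points at a 10% share, and at the planned specificity about 8% of the group would be index-positive, so their days would not count as avoidable.

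5. *How indication is tabulated belongs in the analysis plan.* This stands only in part. A breakdown by indication could be left there. The rule that necessity is derived from the reference standards is stated in the protocol itself, in 5.2 and 11.4.1, and that rule misclassifies these patients.

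**Conclusion.** The concern holds as a misclassification in secondary outcome (iii) and in the modelled benefit. The protocol admits patients treated for superficial or urinary Candida infection and judges the necessity of their treatment by standards that do not assess it.

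The main consequence is in the avoidable days and the modelled benefit: about 2%, 5% or 10% of non-infected patients' avoidable days at assumed shares of 2%, 5% or 10%, given equal treatment length and 92% specificity. The effect on the unnecessary proportion depends on the denominator. At a 10% share it lies between 86% and 95.5%, against 96.0% as written. All these figures rest on a share that the protocol does not give.

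The primary NPV analysis is not threatened. No view is taken on whether treating such infections systemically is clinically right. The change is worth making because a named outcome and both models use the label.

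**What to change.** Leave eligibility and care as they are.

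- Confirm that the baseline indication item separates suspected or confirmed invasive Candida infection from non-invasive infection. If it does not, add that response category.
- In outcome (iii), report a separate category: treated for a non-invasive Candida indication, not assessable by the reference standards.
- Keep this category out of the unnecessary count, the avoidable-day count and the benefit in the 11.4.1 and 11.4.2 models.
- State which denominator the unnecessary proportion uses, whether all treated patients or only assessable ones.

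Repeating the main accuracy analysis without this group is optional, since NPV barely moves.

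The cost is one reporting category, a check of one data item, and wording changes in 5.2 and 11.4. The reported proportion and the avoidable days would be somewhat less favourable to the tests.

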## 6. STUDY DESIGN

## 6.1 Study Design

This is a multi-centre, prospective, diagnostic test accuracy study.

## 6.2 Study Setting

At least 35 adult and paediatric intensive care units (ICU) across the UK will participate. They will range in size and scope from smaller general ICUs to larger specialist units.

## 6.3 Study Schematic Diagram

[figure not shown]

Figure 1: Study Schematic for the A-Stop study

Doc No: TM09-LB01

## 6.4 Study Timeline

Table 1: Study Timeline Gantt Chart

Table 1. Olda	Study Timeline Ganit Chart															_																														
Year					1		2												3									4									5								6	
Quarter		Q	1	Q	2	Q:	3	Q	4	Q5 Q6					Q7 Q8			Q9 Q10			0	211	11 Q12		Q13		Q14		Q15			Q16		Q17		Q18		Q19		Q20		)	221	Ī		
Trial stage	Pre-award	Ş	et-	up			li	nte	rna	al F	l Pilot					Main Trial																		С	los	e-d	own	ı								
Assay validation	Χ	ХХ	X	Х	Χ																																									]
Recruit staff	Χ	ХХ																																												brack  brack
Ethics approval	Χ	ХХ	X	XΧ																																										brack  brack
Sponsorship	Χ	ХХ	X	Χ																																										]
Local R&D approvals	Χ	ХХ	X	ХΧ	X	ХΧ	X	ХХ	(X	X	X >	( X	Χ	Χ																																]
Site initiation		ХХ	X	ХΧ	X	ΧX																														ХΧ	Χ									]
Recruitment					)	ΧХ	X	ХΧ	(X	X	X)	( X	Χ	X)	ΧX	Χ	XΣ	(X	X	Х	Χ	X)	( X	X	ΧX	X	ΧХ	X	ΧX	XX	(X	X	XΣ	( X	Χ	ХΧ	Χ	X)	( X	Χ	X)	(				]
No of sites open						0		8	}	2	1.1		27		33	3	3	4	(°)	5	3	38		39		41		0		32		40		40		4(	)	4	4	4	14					]
Accrual projection						0		0	)	4	8	ĺ	120		22	0	33	8	4	59	5	74	6	370	-	745		745	7	81*	8	33*		903	*	100	8*	112	28*	12	250					]
Study assessments						ΧX			(X		X)	(X		_	XΧ									X		X	ΧX	X	ΧX	X				( X	_	ХХ	Χ	X)	( X	Χ	X)	(X				
Data entry					)	ΧX					χ)	(X	Χ	X)	XΧ	Χ	XΣ	(X	X	Х	Χ	X)	( X	X	ΧX	X	ΧX	X	ΧX	X>	( X	X	XΣ	( X	Χ	ХΧ	Χ	X)	( X							
TMG meetings	Χ	ХХ	X	XΧ	X	ΧX	X	ХΧ	(X	X	X)	(X	Χ	X)	XΧ	Χ	XΣ	(X	X	Х	Χ	X)	(X	X	ΧX	X	ΧX	X	ΧX	X>	( X	X	XΣ	( X	Χ	Х	Χ	X)	(X	Χ	X)	(X	X	Х	ХХ	ί
TSC meetings				Χ										Χ								$\rangle$	(							>	(										)	(				l
Site close-down																																										Χ	X	Χ		
Data analysis														X)	X																												X	ХХ	Χ	
Economic modelling																																						)	(X	Χ	X)	X	Χ	ХΧ		
Report-writing										Ш																		Ш															Ш	Χ	ХХ	
Dissemination					Ш					Ш		$\prod$									$\coprod$					Ш		Ш						Ш									Ш		ХХ	ί

## 6.5 Internal Pilot Study

An internal 12 month pilot study in at least 24 sites will precede the main trial and will follow the processes described in the main study below. The pilot will be used to confirm screening, consent procedures, recruitment rates, data collection, protocol compliance and ensure follow-up processes run smoothly. Patients enrolled in the pilot will be included in the analysis of the main study. Progression to the main trial will be dependent on recruitment and at the discretion of the funder.

#### 6.6 Qualitative risk preferences

A qualitative evaluation of the risk preferences of a sample of patients and clinicians regarding the use of rapid diagnostic tests to discontinue presumptive antifungal therapy is detailed in Appendix 1.

#### 6.7 End of Study

For the purposes of submitting the end of trial notification to the Sponsor and Research Ethics Committee (REC) the end of trial will be considered to be when database lock occurs for the final analysis. The trial will be stopped prematurely if:

- Mandated by the Research Ethics Committee (REC)
- Mandated by the Sponsor (e.g. following recommendations from the Trial Steering Committee (TSC)
- Funding for the trial ceases

The REC originally providing a favourable opinion of the trial will be notified in writing once the trial has been concluded or if terminated early

## 7. PATIENT ELIGIBILITY, SCREENING AND RECRUITMENT

#### 7.1 Eligibility Criteria

Doc No: TM09-LB01 Protocol Version 8.0 Final\_27.05.2021 Page 18 of

Patients will be screened for eligibility based on the inclusion/ exclusion criteria outlined below. Eligibility to participate in the trial will be confirmed by a person suitably qualified by education, training or experience and named on the delegation log.

#### 7.1.1 Inclusion criteria:

- 1. Adults and children >4 weeks old.
- 2. Admitted to a UK ICU (level 2 or 3).
- 3. Prescribed systemic antifungal therapy, for suspected or confirmed Candida infection, during the preceding 24 hours.

#### 7.1.2 Exclusion criteria:

- 1. More than 24 hours systemic antifungal therapy in the preceding 7-days.
- 2. Treatment with antifungal therapy for proven or suspected mould infection (e.g. aspergillosis).
- 3. Neutropenia (absolute neutrophil count <0.5x10^9/L) during preceding 28 days.
- 4. Acute leukaemia or within 12 months of bone-marrow transplantation.
- 5. Hospitalised prisoners.
- 6. Previously enrolled in this study.
- 7. Proven or suspected active infection with COVID- 19.

#### 7.2 Co-enrolment Guidelines

Patients enrolled in any other studies are potential candidates for this study. This is at the Principal Investigator's (PI) discretion and should be considered when the burden on participants is not expected to be onerous. Co-enrolment with any studies should be documented in the Case Report Form (CRF).

#### 7.3 Screening Procedure

Adult and paediatric patients admitted to ICU who are started presumptively on systemic antifungal therapy for Candida infection, are potentially eligible for this study and will be screened regularly, on the basis of the inclusion/exclusion criteria as specified in the protocol. Only those meeting the inclusion criteria should be recorded on the screening log.

All screening data must be recorded via electronic data capture (EDC) which must be completed by the PI or designee to document all patients screened for the study and all patients recruited. Patients screened and not recruited on to the study will be documented via EDC, including the reason(s) for not being enrolled on the study. The PI or designee will be required to submit screening data to the CTU approximately every month.

